### **Propensity Score Stratification**

If the final matched sample size does not meet the aforementioned criterion, then propensity score stratification will be used. Propensity score stratification method has been reported to eliminate 85% to 90% of the treatment bias in observational cohorts. The estimated propensity scores for each patient will then be grouped into 10 strata based on deciles of the propensity score distribution. The frequencies of patients from each cohort will be summarized by strata to ensure sufficient number of patients from each cohort for comparisons.

Prior to initiating the outcome analysis, the quality and assumptions of the propensity score adjustment (matching or stratification) will be evaluated (e.g., using significance testing, assessment of standardized differences, and side-by-side boxplots or histograms). As a rule of thumb, standardized differences greater than 0.10 indicate imbalance that may require further investigation. The propensity model will be finalized prior to initiating analysis of the outcome measures.

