# 9.6.4. Propensity Score Creation

The propensity score adjustment methodology has been widely used in observational studies for causal inference ever since it was introduced by Rosenbaum and Rubin in 1983. Propensity score matching will be the primary analysis. However, if propensity score matching cannot produce balanced matched cohorts with at least 90% of the prasugrel sample, then propensity score stratification will be considered.

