### 9.6.5. Propensity-Adjusted Outcomes Analyses

### 9.6.5.1. Analysis of Categorical Outcomes

Categorical outcomes variables associated with the secondary objectives including rates of rehospitalization (disease-related and all-cause), bleeding, switching, discontinuation, and all-cause mortality may be assessed as follows: If propensity score matching method is implemented, the correlation for paired sample will be considered in the statistical methods. However if propensity score stratification method is implemented, PROC GENMOD model controlling the propensity score strata may be applied. The interaction between propensity score strata and the treatment will also be examined. If the interaction term turns out to be significant, the relative risk in each stratum will be outputted to examine the variability across the strata.

Cohort differences will be summarized using both the estimated relative risk and risk differences from this model. The number needed to treat (NNT) and number needed to harm (NNH) will be defined as the inverse of the risk difference (1/risk difference).

 <sup>26 Austin PC, Grootendorst P, Anderson GM. A comparison of the ability of different propensity score models to balance measured variables between treated and untreated subjects: A Monte Carlo study. *Statistics in Medicine*. 2007;26:734–753. doi: 10.1002/sim.2580
  Austin PC, Mamdani MM. A comparison of propensity score methods: A case-study estimating the effectiveness

<sup>27 Austin PC, Mamdani MM. A comparison of propensity score methods: A case-study estimating the effectiveness of post-AMI statin use. *Statistics in Medicine*. 2006;25:2084–2106. doi: 10.1002/sim.2328

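### If matching fails, the stated secondary-outcome models adjust for ten propensity deciles with no individual covariates, leaving a modest residual confounding that the pooled balance check can miss

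*Protocol*

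**What the plan says.** Section 9.6.4 of the Protocol makes matching (1:1 to 1:3) the primary adjustment and sets the condition for leaving it: "if propensity score matching cannot produce balanced matched cohorts with at least 90% of the prasugrel sample, then propensity score stratification will be considered". The subsection on stratification restates this as "If the final matched sample size does not meet the aforementioned criterion, then propensity score stratification will be used". It then fixes the method: "The estimated propensity scores for each patient will then be grouped into 10 strata based on deciles of the propensity score distribution". On how well this works it says only "Propensity score stratification method has been reported to eliminate 85% to 90% of the treatment bias in observational cohorts".

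The checks come before any outcome analysis. For numbers: "The frequencies of patients from each cohort will be summarized by strata to ensure sufficient number of patients from each cohort for comparisons". For balance: "As a rule of thumb, standardized differences greater than 0.10 indicate imbalance that may require further investigation". For timing: "The propensity model will be finalized prior to initiating analysis of the outcome measures".

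The outcome models under stratification are in section 9.6.5:
- Categorical secondary outcomes (9.6.5.1): "PROC GENMOD model controlling the propensity score strata may be applied". The stratum-by-treatment interaction is also examined.
- Utilization, costs and treatment patterns (9.6.5.2, item 2): the listed terms are cohort, strata and their interaction.
- Primary MACE (9.6.5.2): a multivariate Cox model whose terms are not listed.

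**The concern.** Stratification puts patients with different scores into the same cell and treats them as comparable. Inner deciles are narrow, so little is lost. The two outer deciles are open-ended, and residual imbalance collects there. The fallback is reached because the cohorts could not be matched well, so its outer deciles are likely to be wide. They also receive the hard-to-match patients whom matching would have set aside.

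A model with strata alone cannot remove differences inside a decile, whereas the individual covariates could. A standardized difference averaged over ten strata can look acceptable because eight of them are nearly balanced.

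Direction matters as well. Section 7 reports from another database that prasugrel patients were younger and had fewer comorbidities associated with bleeding. Leftover confounding would therefore plausibly favour prasugrel, which is the hypothesised direction in section 8.

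**Working it through.** **Inputs.** Table 2: n1 = 5,101 prasugrel and n0 = 21,548 clopidogrel, so r = n0/n1 = 4.224 and p = 5,101/26,649 = 0.191. Section 9.4: 12% one-year MACE, two-sided 5%. Section 9.6.4: 90% retention, ten deciles, 0.10 rule of thumb. The protocol gives no overlap figures for this database, so separation is an assumption: the score is N(0,1) in clopidogrel and N(d,1) in prasugrel, with c = Φ(d/√2).

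**1. The cited 85-90%.** In this model five strata leave about 10-12% of the score difference for d up to 1 (overall or fixed-effect weights), in line with the cited removal. Ten strata leave 4-5% with those weights. The cited figure therefore behaves like a five-stratum result.

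**2. When retention falls below 90%.** The best exact 1:k retention is Φ(x* − d) + (r/k)[1 − Φ(x*)], with x* = d/2 + ln(r/k)/d.
- d = 0.90, k = 1: x* = 2.051, giving 0.875 + 4.224 × 0.0201 = 96.0%.
- d = 1.13, k = 1: x* = 1.840, giving 0.761 + 4.224 × 0.0329 = 90.0%. Here c = Φ(0.799) = 0.79.
- The 90% point is at d = 0.79 (c = 0.71) for 1:2 and at d = 0.54 (c = 0.65) for 1:3.

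**3. Balance in deciles at the 1:1 threshold (d = 1.13).** Cut points are deciles of the pooled score. Cohort differences are in whole-cohort SDs.

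| Decile | 1 | 2 | 3 | 4 | 5 | 6 | 7 | 8 | 9 | 10 |
|---|---|---|---|---|---|---|---|---|---|---|
| Difference | 0.152 | 0.019 | 0.011 | 0.008 | 0.007 | 0.007 | 0.009 | 0.012 | 0.023 | 0.221 |

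The top decile holds 31% of prasugrel patients. Scaled by the SD inside the decile, the outer differences are larger, 0.41 and 0.49.

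Pooled over deciles:
- equal weights: 0.468/10 = 0.047;
- fixed-effect weights: 0.055;
- prasugrel weights: 0.079.

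All are below 0.10. Divided by 1.13, they leave 4.1%, 4.8% and 7.0% of the original difference.

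**4. What that does to a test.** Suppose the log hazard is linear in the score, there is no treatment effect, and confounding alone gives HR 0.70 (assumption). The residual shift is 0.04 × ln 0.70 = −0.0143 to 0.07 × ln 0.70 = −0.0250. SE = 1/√[D p(1 − p)], and the rejection rate is Φ(−1.96 + z) + Φ(−1.96 − z) with z = |shift|/SE.

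| Events D | SE | z | False positives |
|---|---|---|---|
| 3,198 (12% of 26,649) | 0.0449 | 0.32 to 0.56 | 6.2% to 8.6% |
| 1,919 (60% of these, assumed) | 0.0580 | 0.25 to 0.43 | 5.7% to 7.1% |

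Over the assumed HR, with D = 3,198: 0.80 gives 5.5-6.4% and 0.60 gives 7.4-12.5%. Rarer outcomes have a larger SE and less inflation.

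**The case against.** The strongest reply is that this is a contingent fallback with several safeguards. Stratum counts and balance are reviewed before outcomes are seen. The stratum-by-treatment interaction is examined for categorical outcomes. Section 9.6.6 offers regression on all final propensity-model variables and a rule-out analysis for unmeasured confounding. An unseen SAP may also list more model terms. Much of this stands, and it keeps the point small. But the section 9.6.6 analyses are optional, stratum counts do not show balance, and the terms in item 2 of section 9.6.5.2 are stated rather than deferred.

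Three stronger readings are tempting, and the documents do not support them:
- **By the protocol's own figure, 10-15% of the bias will remain.** The sentence reports a general finding and names no number of strata. Applying it to ten strata would give 9-22% false positives under the same HR 0.70, but ten strata leave about 4-7% in the model.
- **The primary MACE analysis adjusts for strata alone.** The Cox model is called multivariate and its terms are not listed, so this cannot be concluded.
- **The outer deciles breach the protocol's balance rule.** The 0.10 value is a rule of thumb that prompts further investigation, and it is not set per decile. Single covariates may also differ less than the score does.

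For the trigger, the back-reference to the criterion already given largely resolves the difference. What remains is considered against used, and balance plus retention against sample size. Restricting to common support or splitting the outer deciles involves trade-offs, and their absence is not counted here as an error.

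**Conclusion.** The point holds in a limited form. If the fallback is used, the stratified models stated for secondary outcomes leave within-decile confounding that the individual covariates could reduce, and a pooled 0.10 check would probably not flag it. At the 1:1 threshold the residual is about 4-7% of the measured confounding, with false positives of about 6-9% against a nominal 5% for an outcome as frequent as MACE if confounding alone gave HR 0.70.

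This rests on a normal score with equal variances, a log hazard linear in that score, an assumed strength of confounding, and the preliminary Table 2 counts. If the trigger fires at 1:2 or 1:3, separation and outer-decile imbalance are smaller. Nothing here concerns unmeasured confounding, and nothing shows that the primary Cox analysis is affected.

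**What to change.** 1. In sections 9.6.5.1 and 9.6.5.2 (item 2), state that under stratification the models contain the covariates of the final propensity model in addition to cohort and strata (and the interaction where it is already listed).
2. In section 9.6.5.2, confirm that the multivariate Cox model for MACE includes those covariates together with the strata when stratification is used.
3. Editorial: make the stratification subsection use the trigger from the opening of section 9.6.4 (balance and 90% retention), and choose one verb for what follows.

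The covariates are already collected for the propensity model, so no new data are needed. The cost is a few more parameters, which matters mainly for the rarest outcomes.

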### 9.6.5. Propensity-Adjusted Outcomes Analyses

### 9.6.5.1. Analysis of Categorical Outcomes

Categorical outcomes variables associated with the secondary objectives including rates of rehospitalization (disease-related and all-cause), bleeding, switching, discontinuation, and all-cause mortality may be assessed as follows: If propensity score matching method is implemented, the correlation for paired sample will be considered in the statistical methods. However if propensity score stratification method is implemented, PROC GENMOD model controlling the propensity score strata may be applied. The interaction between propensity score strata and the treatment will also be examined. If the interaction term turns out to be significant, the relative risk in each stratum will be outputted to examine the variability across the strata.

Cohort differences will be summarized using both the estimated relative risk and risk differences from this model. The number needed to treat (NNT) and number needed to harm (NNH) will be defined as the inverse of the risk difference (1/risk difference).

 <sup>26 Austin PC, Grootendorst P, Anderson GM. A comparison of the ability of different propensity score models to balance measured variables between treated and untreated subjects: A Monte Carlo study. *Statistics in Medicine*. 2007;26:734–753. doi: 10.1002/sim.2580
  Austin PC, Mamdani MM. A comparison of propensity score methods: A case-study estimating the effectiveness

<sup>27 Austin PC, Mamdani MM. A comparison of propensity score methods: A case-study estimating the effectiveness of post-AMI statin use. *Statistics in Medicine*. 2006;25:2084–2106. doi: 10.1002/sim.2328

### 9.6.5.2. Analysis of Continuous Outcomes

### Primary objective: One year MACE

In addition to KM curves, multivariate Cox proportional hazards models will be used to assess the primary objective using an *on treatment* approach where patients will be censored at the end of treatment exposure time window (time of discontinuation or switching) and not allowed to switch treatment groups on the basis of their treatment use. If high rates of switching and/or discontinuation (threshold will be specified in the SAP) are observed, then an *as treated* analysis, where patients will be censored at the end of treatment exposure time window but allowed to switch treatment groups on the basis of their treatment use, may be conducted as a secondary analysis. Time-varying treatment exposure and treatment status as a time-dependent covariate may be incorporated into the Cox proportional regression model(s) as appropriate. In addition, an approach where patients will be assigned to the treatment they are first exposed (based on first prescription fill post index hospitalization discharge), regardless of discontinuation or switching, will be used to assess the primary endpoint (up to one year MACE) as a secondary objective.

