#### Discontinuation

Discontinuation of the post-discharge index therapy will be defined by a gap of 30 days or more in fills for the index therapy. The date of discontinuation will be defined by the run-out of days supply of the last prescription filled prior to the first 30-day gap in treatment, if any. The days supply of overlapping fills will be pushed out to start the day after the end of the previous fill's supply.

Discontinued therapy if:

- (End of study period) (run-out date of last fill)  $\ge$  30 days OR
- (start date of fillx+1) (run-out date of fillx 1)  $\ge$  30 days

The total number of fills for the post-discharge index therapy prior to discontinuation will also be calculated.

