TRANSLATE-ACS is an on-going observational study following more than 12,000 MI-PCI patients prospectively. This study is gathering rich clinical data through one year, but requires informed consent and relies on self-report for treatment adherence and cost outcomes. Another recent retrospective cohort study selected ACS-PCI patients on the basis of the prasugrel US prescribing information using the Premier database of hospital discharges. This study found marked differences in the profile of patients receiving prasugrel compared to clopidogrel. Prasugrel patients were younger and had a lower risk of comorbid conditions associated with bleeding. After adjustment for baseline differences, patients using prasugrel, compared to clopidogrel, had a significantly lower rate of MI-related rehospitalization with no increase in the rate of bleeding-related rehospitalization at 30 days and 90 days following the index ACS-PCI hospital discharge. The study also found that patients using prasugrel had significantly shorter length of stay and lower costs with no increased rate of bleeding during the index hospitalization. While results from this study, particularly those related to the reduction in MI, reflect the short term efficacy noted in the TRITON-TIMI 38 trial, long term observational data (> 90 days) comparing the use of these agents in the real world setting is scarce. The current retrospective claims database analysis will help fill this important gap in the literature as well as collect economic data from a large managed care health plan in the US.

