# 8. Research Objectives

The overall hypothesis of this study is that, after adjustment for baseline differences, prasugrel will be associated with a significantly lower risk of major adverse cardiovascular events (MACE) than clopidogrel up to one year post-discharge from the index hospitalization.

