### 8.1. Primary Objectives

1. To compare MACE with prasugrel versus clopidogrel up to one year post-discharge from the index hospitalization.

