### 9.1.4. Study Timeframe

Five observation periods will be defined:

- 1. **Index hospitalization period**: Days between, and including, the admission and discharge dates of the index hospitalization.
- 2. **Baseline period**: 12 months before the index hospitalization admission date.
- 3. **ADP-ri index selection period**: Study index date to 30 days post-discharge from the index hospitalization.
- 4. **Variable follow-up period**: Days on and after the study index date until 3 or more months after the study index date or until death, if sooner. Maximum follow-up will be 12 months.
- 5. **Fixed follow-up period**: Days on and after the study index date until 12 months after the study index period or until death, if sooner. This one year follow-up period will be used to assess the primary endpoint as a secondary objective, adherence, persistence, and costs.

Figure 1 illustrates the study timeframe.

Figure 1. Study Timeframe

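### The primary objective is MACE up to one year after discharge, but the primary Cox model censors at stopping or switching and so estimates MACE while on the index drug; the analysis that matches the objective is only secondary

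*Protocol*

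**What the plan says.** Protocol section 8.1 gives the primary objective: "To compare MACE with prasugrel versus clopidogrel up to one year post-discharge from the index hospitalization". The hypothesis in section 8, meant to hold once the cohorts have been adjusted at baseline, reads: "prasugrel will be associated with a significantly lower risk of major adverse cardiovascular events (MACE) than clopidogrel up to one year post-discharge". Neither is limited to time on treatment.

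Section 9.6.5.2 assigns this objective to multivariate Cox models with an on-treatment rule: "patients will be censored at the end of treatment exposure time window (time of discontinuation or switching". Section 3 fixes the trigger: "Discontinuation of the post-discharge index therapy will be defined by a gap of 30 days or more in fills for the index therapy". The stop is dated back to the run-out of the last supply before the gap. Section 9.8 adds that switches count as discontinuations.

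The full-year comparison by first-filled drug is also committed. In section 9.6.5.2 an assignment by first fill, "regardless of discontinuation or switching, will be used to assess the primary endpoint (up to one year MACE) as a secondary objective". Section 9.1.4 says the same of the fixed follow-up period: "This one year follow-up period will be used to assess the primary endpoint as a secondary objective, adherence, persistence, and costs".

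An as-treated analysis is optional: "If high rates of switching and/or discontinuation (threshold will be specified in the SAP) are observed", it may be run. It also censors at the end of exposure. Propensity matching or stratification (section 9.6.4) uses baseline variables only. The limitations in section 9.8 do not discuss informative censoring.

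**The concern.** Two linked points arise.

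First, the primary analysis and the primary objective ask different questions. One concerns the year after discharge whatever happens to treatment. The other concerns the hazard among patients still filling the index drug. A reader of the headline hazard ratio would take it as the answer to section 8.1, and it is not.

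Second, an ordinary Cox model with this rule assumes that, given its covariates, patients who stop have the same later MACE hazard as those in the same cohort who continue. Balance at baseline does not secure that. If, for example, patients who bleed after discharge are at higher MACE risk and leave one drug faster than the other, the patients remaining on the two drugs are no longer comparable. The hazard ratio then moves without any drug effect behind the movement.

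The rule-out analysis in section 9.6.6 concerns an unmeasured confounder of treatment choice, not selection after baseline. The optional 60-day gap and switch-definition analyses change who is censored and when, but do not model who is censored.

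**Working it through.** **1. The plan's own figure.** Section 9.4 states 92% power for HR 0.85, a 12% one-year clopidogrel rate, a 3:1 ratio and two-sided 0.05. Table 2 gives 5,101 prasugrel patients, hence 3 × 5,101 = 15,303 clopidogrel patients.

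- Prasugrel rate: 1 − 0.88^0.85 = 10.3%.
- Events: 15,303 × 0.12 + 5,101 × 0.103 ≈ 2,362.
- Schoenfeld: |ln 0.85| × √(2,362 × 0.25 × 0.75) − 1.96 = 0.1625 × 21.04 − 1.96 = 1.46, so power is 92.8%.

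The stated figure reproduces. It is built on a one-year rate with no allowance for censoring at treatment stop.

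**2. Effect of the rule on events.** The protocol gives no stopping rate, so d is assumed. Stopping here is unrelated to risk and equal in both cohorts. With λ = −ln 0.88 (times 0.85 for prasugrel) and g = −ln(1 − d), the expected event proportion per cohort is λ/(λ + g) × (1 − e^−(λ+g)).

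| Stopped by one year (assumed) | Events | Power |
|---|---|---|
| 10% | 2,244 | 91.5% |
| 20% | 2,122 | 90.0% |
| 30% | 1,994 | 88.1% |
| 40% | 1,859 | 85.9% |
| 50% | 1,716 | 83.0% |

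The loss of power is modest.

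**3. Possible bias.** All values in this step are assumed except the 12% rate, HR 0.85 and the 3:1 ratio. There are two risk groups, balanced at baseline, and the Cox model does not see the group. In the base case, 30% of patients are high-risk with MACE hazard ratio 2. The stopping hazard is 0.4 per year, except 0.8 for high-risk prasugrel patients.

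- Low-risk hazard λ solves 0.7(1 − e^−λ) + 0.3(1 − e^−2λ) = 0.12, giving λ = 0.0991.
- Stopped at one year: clopidogrel 1 − e^−0.4 = 33%; prasugrel 1 − (0.7e^−0.4 + 0.3e^−0.8) = 40%.
- High-risk share still at risk at 12 months under HR 0.85: clopidogrel 0.1649/(0.1649 + 0.4250) = 28.0%; prasugrel 0.1139/(0.1139 + 0.4313) = 20.9%.
- Solving the large-sample Cox score equation gives HR 0.828 on treatment, against 0.851 with no stopping.
- Bias: ln(0.828/0.851) = −0.027, and 0.027/0.1625 = 17% of the assumed log effect.

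| Scenario | HR when true effect is 0.85 | HR when no true effect |
|---|---|---|
| Base case | 0.828 | 0.973 |
| High-risk prasugrel stopping 0.6 | 0.839 | 0.986 |
| 20% high-risk | 0.832 | 0.979 |
| Risk ratio 3 | 0.815 | 0.957 |
| Risk ratio 3, stopping 0.5 vs 1.0 | 0.807 | 0.948 |
| Base case, faster leavers on clopidogrel | 0.875 | 1.028 |
| High-risk stop equally fast in both | 0.851 | 1.000 |
| Any of the above, model stratified on the risk group | 0.850 | 1.000 |

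For scale, about 1,920 events remain in the base case, so the standard error of the log HR is 1/√(1,920 × 0.1875) ≈ 0.053. The bias there is about half a standard error (0.3 to 1.0 across the scenarios with unequal risk-related stopping).

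**4. A second set of assumptions.** Take 20% high-risk, risk ratio 3 and 30% of low-risk patients stopping. If high-risk patients stop two or three times as fast on prasugrel only, the HR is 0.82 or 0.80 (0.97 or 0.94 with no effect). If on clopidogrel only, it is 0.88 or 0.91 (1.03 or 1.07). Stopping that differs by cohort but is unrelated to risk (30% vs 40%) gives 1.00 with no effect.

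**The case against.** The strongest reply is that the study already contains the right analysis. Section 9.6.5.2 commits to the first-treatment comparison, and on-treatment is a recognised, openly declared choice. This stands to the extent that a reader who infers that the study leaves its objective unanswered would be wrong. What remains is that the matching analysis is labelled secondary while the headline result estimates something else.

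A second reply is that bias is not shown. This also stands. A reader might infer that the cohorts will drift apart, or that the result will favour prasugrel. The documents support neither, since they give no discontinuation rates. Section 7 reports from another database that "Prasugrel patients were younger and had a lower risk of comorbid conditions associated with bleeding", but that describes who was prescribed the drug, which is what the propensity score addresses. It does not describe who stops. Objectives 7 and 8, on predictors of stopping and its link to outcome, apply only if treatment patterns are found to differ.

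Third, the planned Cox model is multivariate. To the extent that its covariates capture MACE risk, the bias shrinks; conditioning on the risk group removes it. What survives is unmeasured or time-updated risk, such as a bleed after discharge. The calculation treats the risk factor as fixed and unseen, so it stands in for that case only roughly.

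Fourth, censoring weights may be in the SAP, which is not at hand. But no SAP detail makes an on-treatment hazard match an objective without that condition. The choice of primary and secondary is fixed in the protocol.

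**Conclusion.** The mismatch is established from the text: sections 8 and 8.1 concern MACE up to one year, the primary model in section 9.6.5.2 concerns MACE while on the index drug, and the matching analysis is secondary.

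The bias is a risk of unknown presence and direction. It requires stopping to depend on MACE risk differently by cohort, beyond the model covariates. Under the first set of assumptions in the working, with the risk factor wholly unmeasured, the on-treatment HR would be about 0.81 to 0.87 against 0.85, or 0.95 to 1.03 with no true effect. The second set gives 0.80 to 0.91 and 0.94 to 1.07. These are illustrations on both sides of the true value, and the bias is nil under equal or fully captured risk-related stopping. The stated 92% power is not in dispute. This is a change that should be made, not a defect that invalidates the study.

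**What to change.** 1. State in sections 8.1 and 9.6.5.2 that the on-treatment model estimates MACE while on the index drug.
2. Let the conclusion about MACE up to one year after discharge rest on the first-treatment analysis already planned. Run it in all eligible patients, censoring at disenrolment or end of data. Section 9.1.4 appears to tie it to a full 12 months of follow-up or death, whereas section 9.1.2.1 requires only 3 months of enrolment. Restricting it to patients enrolled for 12 months would add a selection of its own, so the wording of section 9.1.4 should be aligned.
3. Beside the on-treatment model, report a version weighted by the inverse probability of remaining uncensored. Estimate the weights separately by cohort from baseline covariates and time-updated claims recorded before censoring (for example bleeding encounters, transfusions and hospitalizations), with robust variance. Whether the weighted model should be the sole primary analysis is debatable and is not needed here.

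The cost is one censoring model per cohort from claims already held, some loss of precision from the weights, and wording changes. No new patients or data are needed. The first-treatment comparison keeps about 2,362 events and 92.8% power if all patients are followed for the year and HR 0.85 still applies. Enrolment shorter than 12 months would lower the event count, and follow-up after stopping or switching may dilute the effect.
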